3.3.1.4 On-treatment and During Period definitions

An event, or measurement, is said to be occurring during a particular period if the start date of the event, or the date of measurement, falls within the start and end date of the period as defined in Section 3.3.1.3.

An event, or measurement, is said to be occurring on-treatment for a particular period if the start date of the event, or date of measurement, falls within this period and simultaneously occurs between the first dose date and last dose date of SZC/Placebo, for that period, plus one day.

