    - The participant may remain on the other study intervention. See NOTE.
    - The participant should attend an ED visit.
    - The participant must remain in the study and attend all subsequent visits as planned.
  - If both SZC/placebo and lisinopril/valsartan are discontinued:
    - The participant should attend an ED visit.
    - It is preferred that the participant remain in the study and attend all subsequent visits as planned.
    - If the participant is unwilling to remain in the study and attend all subsequent visits as planned, it is acceptable to offer modified follow-up. Modified follow-up options include, but are not limited to, modified visit schedule, telephone contact, or allowing the investigator to check medical records for information about the participant's health status.

NOTE: Participants who are started on lisinopril and who subsequently develop any common nonserious side effects (eg, cough), can change to valsartan at a comparable dose range per Appendix B 1 at the investigator's discretion. If this happens, the participant will complete an ED visit when lisinopril is permanently discontinued. The participant can continue to receive SZC/placebo (and valsartan) in the study.

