3.2 Analysis Populations

The study consists of five analysis populations, namely:

Populations for Analysis

| Population/analysis set | Description |
|---|--|
| Enrolled | All participants who sign the ICF. |
| Safety analysis set, initiation phase (SAS-IP) | All participants receiving at least one dose of Initiation SZC. |
| Safety analysis set, run-in phase (SAS-RIP) | All participants receiving at least one dose of Run-in SZC, regardless within or without the run-in phase. |
| Safety analysis set, maintenance phase (SAS-MP) | All randomized participants receiving at least one dose of Maintenance SZC or Maintenance-phase placebo, regardless within or without the maintenance phase. |
| Full analysis set (FAS) | All randomised participants. |

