3.3.1.3 Study Periods

The study consists of five distinct study periods, namely: Screening phase, Initiation phase, Run-In phase, Maintenance phase and Follow-Up phase. Participants will transfer directly between study periods in the order given.

The five phases are delimited in time like this:

Screening phase

- *First day*: the day of the date of signature on the signed informed-consent form (ICF).
- *Last day* (if participant not going into Intervention period/Initiation phase): the day of last contact.
- *Last day* (if participant going into Intervention period/Initiation phase): the day before first Initiation-phase S2C-dose.

Note: If there is no signed ICF, then there is no Screening phase, and no other phases either.

Initiation phase

- *First day*: the day of first Initiation-phase S2C-dose.
- *Last day* (if not going into Run-in phase): the day of last Initiation-phase S2C-dose.
- *Last day* (if going into Run-in phase): the day before the first day of the Run-in phase (see below).

Run-in phase

- *First day*: the day of first Run-in SZC dose, or the day of first Run-in (IP) RAASI-dose, whichever comes first, however no earlier than the day after last Initiation-phase SZC-dose.
A consequence of this is that the Run-in phase always has its first day on the day after last Initiation-SZC dose, *at the earliest*; if any Run-in IP (SZC, lisinopril, valsartan, irbesartan), would be initiated before, or on the same day as, the last Initiation SZC dose, then the Run-in phase will start on the day after the day of last Initiation-SZC dose. This means that any Initiation-SZC dosing takes precedence over any Run-in IP dosing when it comes to separating the Initiation phase and the Run-in phase, in favour of the Initiation phase. If – on the other hand – both Run-in SZC and Run-in RAASI would start on a day (potentially different days for Run-SZC and Run-in RAASI) *after* the day of last Initiation SZC then the Run-in phase will have its first day on the day of the earliest initiation of any of the two Run-in IP types (SZC or RAASI). This means that any time “gap” between Initiation SZC and Run-in IP will be assigned to the Initiation phase.
- *Last day* (if not going into Maintenance phase): the day of last Run-in SZC-dose, or the day of last Run-in (IP) RAASI-dose, whichever comes last.
- *Last day* (if going into Maintenance phase): the day before the day of randomisation.

Maintenance phase

- *First day*: the day of randomisation.

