4.1.1 Subject Disposition and Recruitment

4.1.1.1 Definitions and Derivations

Subject disposition will be collected as part of the eCRF. The following definitions and derivations are applicable for the table:

- **Enrolled** subjects will be defined as those who have signed the informed consent form.
- Subjects who **entered the initiation phase** will be defined as those who received at least one dose of Initiation SZC.
- Subjects who **entered the run-in phases** will be defined as those who received at least one dose of Run-in SZC or Run-in RAASi (lisinopril/valsartan/irbesartan).
- Subjects who **entered the maintenance phase** will be defined as those who were randomized.
- Subjects who **completed a phase of the study** will be defined as subjects who either are assigned the status "Completed" for the phase by the investigator, or who have a

disposition status as per the eCRF (e.g., "Death", "Withdrawal by subject") that is assigned during a later phase.

- Subjects who **completed the study** will be defined as subjects who completed all these four phases:
 - the Screening phase,
 - the Initiation phase,
 - the Run-in phase, and
 - the Maintenance phase,and, in addition, attended the follow-up visit.
- Subjects who **completed treatment** for a given phase will be defined as subject who did not discontinue treatment prematurely during that phase. Note that, for the initiation and run-in phases, this should coincide with completion of that whole phase, as subjects who discontinue treatment during these phases should also discontinue the whole study as per the study design.

The study period during which a particular disposition event takes place is also indicated directly in the eCRF by the investigators and will be used in the presentations.

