4.1.2 Analysis Sets

4.1.2.1 Definitions and Derivations

There will be five separate analysis sets in the study. For the definition, see Section 3.2. Explicitly, the FAS set will consist of all patients receiving a randomization number, while the different SAS sets will be determined by whether a patient has at least one dose of SZC provided to them, as per the drug accountability module in the eCRF, during the respective phases of the study.

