4.5.1.2 Presentations

Adverse events (AE) will be summarised descriptively in accordance with the rules described in Section 3.3. Estimates of differences in AE profiles (e.g., hazard ratios, difference in probability of an event occurring within a pre-specified time interval) may also be presented, along with the corresponding CIs.

All AEs will be summarised by SOC and PT according to the latest MedDRA version available at the time of database lock.

Overall overview

An AE overview table will be created, with AEs falling within the following categories summarized by treatment group.

- Any AE
- Any SAE

- Any AE with outcome death
- Any AE leading to discontinuation of SZC or SZC/placebo
- Any AE leading to discontinuation of Lisinopril/valsartan
- Any AE leading to dose interruption of SZC or SZC/placebo
- Any AE leading to dose interruption of Lisinopril/valsartan
- Any AE leading to dose reduction of SZC or SZC/placebo
- Any AE leading to dose reduction Lisinopril/valsartan
- Any AE possibly related to SZC or SZC/placebo
- Any AE possibly related to Lisinopril/valsartan
- Any SAE possibly related to Lisinopril/valsartan
- Any SAE possibly related to SZC or SZC/Placebo

AEs, SAEs, DAEs and deaths, by system organ class and preferred term

A detailed overview of number, and percentage, of subjects with AEs, SAEs, DAEs and deaths in a particular SOC and PT class will be presented.

Most common AEs

A tabulation of the PT terms sorted by decreasing frequency (most common AEs in SZC arm on top) will be provided.

Intensity of AEs

An overview of the number and the percentage of subjects with AEs in a particular SOC, PT and intensity class (mild, moderate, severe) will be created. Subjects will be counted only once in each category. A subject with two AE in the same SOC and PT class of, e.g., both high and moderate intensity will be assigned the “high” intensity category, i.e., the more severe class.

Causality of AEs

Number and percentage of subjects with AEs considered as possibly related to each of the IPs (SZC/Placebo and Lisinopril/valsartan) will be tabulated by SOC and PT, in separate tabulations.

Events related to oedema, hypokalaemia, or hyperkalaemia

An overview of oedema-related AEs, with number and percentage of subjects with an event with a particular PT term, will be presented.

Number of subjects with AE classified as hypokalaemia, hyperkalaemia, or hyperkalaemia requiring rescue, will be tabulated in a similar manner.

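### SAS-RIP requires a Run-in SZC dose although run-in can start with RAASi alone, so a RAASi-only participant's run-in adverse events reach no phase-specific safety table

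*SAP*

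**What the plan says.** **Run-in phase.** SAP 3.3.1.3 makes the first day of run-in "the day of first Run-in SZC dose, or the day of first Run-in (IP) RAASI-dose, whichever comes first", but never earlier than the day after the last initiation SZC dose. It foresees that the two drugs may start on different days. For a participant who is not randomised, the phase ends with the later of the two last doses. SAP 4.1.1.1 uses the same either-drug rule for disposition: participants who entered run-in are "those who received at least one dose of Run-in SZC or Run-in RAASi (lisinopril/valsartan/irbesartan").

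**Run-in safety set.** SAP 3.2 defines SAS-RIP as "All participants receiving at least one dose of Run-in SZC, regardless within or without the run-in phase". SAP 4.1.2.1 repeats the single-drug basis: the safety sets are "determined by whether a patient has at least one dose of SZC provided to them", read from the drug accountability module. Protocol Table 12 is also SZC-only.

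**Tables.** SAP 4.5 builds the safety tables on the safety sets, by phase, and as a rule both On Treatment and During Study. Follow-up events go to the phase just before.

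**On-treatment window.** SAP 3.3.1.4 requires that the start date "falls within this period and simultaneously occurs between the first dose date and last dose date of SZC/Placebo, for that period, plus one day". RAASi dates play no part. SAP 4.5.1.2 nevertheless plans RAASi-specific rows, such as "Any AE leading to discontinuation of Lisinopril/valsartan", with others for interruption, reduction and relatedness. Protocol 7.1.1.1 says of a maintenance participant who stops one of the two interventions: "The participant may remain on the other study intervention".

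**The concern.** Lisinopril and valsartan are study intervention under Protocol Section 6 and are listed as IMP in Table 5. The SAP uses their dosing to decide when run-in begins and who entered it, but not to decide whose run-in safety data are tabulated. Phase, disposition and analysis set should fit together, so that each adverse event dated in a phase belongs to someone in that phase's safety set. For run-in they do not. At stake are the completeness of the run-in adverse event tables and agreement between the disposition count and the safety denominator.

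The on-treatment window shows a milder form of the same mismatch: rows about lisinopril/valsartan carry a treatment label set by the dates of another product.

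**Working it through.** The plan gives no figure on this point. The check applies its date and set rules side by side.

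| Rule | Qualifying dose |
|---|---|
| Run-in phase starts (SAP 3.3.1.3) | Run-in SZC or Run-in RAASi |
| Entered run-in (SAP 4.1.1.1) | Run-in SZC or Run-in RAASi |
| In SAS-RIP (SAP 3.2, 4.1.2.1; Protocol Table 12) | SZC only |
| On-treatment (SAP 3.3.1.4) | SZC/placebo only |

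**Case A, run-in.** A participant takes initiation SZC, then Run-in RAASi, and never takes Run-in SZC.

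1. Run-in starts on the first RAASi day after the last initiation SZC dose. The initiation phase ends the day before.
2. Disposition counts the participant as having entered run-in.
3. The participant is in the initiation safety set (SAS-IP) but not in SAS-RIP.
4. An adverse event starting in run-in is dated outside the initiation phase, so the initiation tables do not hold it. The run-in tables are built on SAS-RIP, so they do not hold it either, On Treatment or During Study.
5. An event after the last RAASi dose in a non-randomised participant falls in follow-up, is assigned to run-in, and drops out in the same way.
6. What remains is a listing. SAP 4.5 allows listings for all enrolled participants, and 4.5.1.2 names a listing of all adverse events among those that may be provided.

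**Case B, maintenance (day numbers are illustrative).** Last SZC/placebo dose on Day 100, lisinopril to Day 400.

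- Window closes: 100 + 1 = Day 101.
- RAASi-exposed days outside it: Days 102 to 400, that is 400 − 102 + 1 = 299 days.
- A lisinopril-related event on Day 200 is missing from the on-treatment row. It stays in the During Study table, because maintenance runs to last contact (SAP 3.3.1.3).

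Temporary interruptions of SZC/placebo do not create this gap, because the window runs from first to last dose.

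**Case C, run-in with staggered starts (illustrative).** If RAASi starts 2 days before Run-in SZC, events on those 2 days are not on-treatment. The participant is in SAS-RIP, so the During Study table keeps them.

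Only Case A removes events from every phase-specific table. Cases B and C affect the label alone.

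**The case against.** **The set follows the protocol.** Protocol Table 12 defines SAS-RIP by SZC, and the SAP keeps that criterion. This stands, and it means the fix is a departure to be logged. It does not remove the mismatch, because the SAP's own run-in start and entry rules go beyond SZC.

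**Case A is an edge case.** Run-in participants are meant to receive SZC and lisinopril/valsartan together, and Protocol 7.1.1.1 requires both to stop if either is permanently discontinued in run-in. RAASi continuing alone is therefore permitted only in maintenance. This stands as to frequency. Section 4.1.2.1 also speaks of SZC provided, so someone supplied with Run-in SZC who never took it might still be in the set. How that wording was applied is uncertain, since the amendment history reports accountability data as unavailable for compliance.

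**An SZC/placebo window suits the objective.** The safety objective compares SZC with placebo, and Table 5 gives the use of lisinopril/valsartan as background. Two windows within one overview table would also make its rows less comparable. This stands, and the window should remain the main definition.

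**Stronger readings that the documents do not support.** A reader might infer that maintenance RAASi events are lost. They are not; the During Study tables hold them. Events that lead to a RAASi change normally presuppose current RAASi treatment, causality is judged separately for each intervention, and the listings carry planned doses of both. A reader might also assume that 10–20% stop SZC/placebo halfway and stay on RAASi, giving 0.10–0.20 × 0.5 = 5–10% of RAASi exposure off-treatment. That product only restates its assumptions. Nor does a between-arm bias follow. Chronic use of another binder ends SZC/placebo, and might be commoner on placebo, but the hyperkalaemia instructions in Protocol 6.6.4 also reduce, pause or stop RAASi, which works the other way.

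**Conclusion.** The run-in point holds as an internal inconsistency in the SAP. A participant treated in initiation who then takes Run-in RAASi but no Run-in SZC is counted as entering run-in, is outside SAS-RIP, and has run-in adverse events in no phase-specific safety table. The conclusion rests on reading 3.2 as written, with an SZC dose required. The number affected is probably small, since both drugs are planned from the start of run-in; the documents give no count and do not show that such a participant exists.

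The on-treatment point is one of labelling, confined to the lisinopril/valsartan-specific rows and chiefly to maintenance. It is not an error in the SZC-versus-placebo comparison. Both points are minor and neither touches the efficacy analyses.

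**What to change.** **Run-in set.** In SAP 3.2, define SAS-RIP as all participants with at least one dose of Run-in SZC or Run-in RAASi (lisinopril, valsartan or irbesartan). Conform 4.1.2.1, which repeats the SZC-only basis. Record the change as a departure from Protocol Table 12, as the amendment history already does for an earlier revision of 3.2. The cost is SAP wording and a slightly larger set that includes a few participants with no Run-in SZC. If the SZC-only basis is intended, say so and state where RAASi-only run-in events will be reported.

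**On-treatment rows (optional).** Keep the SZC/placebo window as the main definition. Either footnote the lisinopril/valsartan rows to say that on-treatment refers to SZC/placebo dates, or add a supplementary flag for those rows based on RAASi dose dates. The footnote costs nothing. The flag can use the RAASi dosing dates already recorded, but should be shown apart from the main overview so that rows there stay comparable.

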3.3.2 Visit Window

Visit windowing will not be applied for the study. Rather, the assignment of measurements to scheduled visits will be determined by the investigator. Missing measurements at scheduled visits will not be replaced with those obtained on the unscheduled visits in the vicinity of the scheduled ones.

3.3.3 Handling of Unscheduled Visits

Data obtained on unscheduled visits (e.g., safety laboratory evaluations) will be excluded from any analyses and presentations that are based on scheduled visits, an example of these being a presentation summary statistics of laboratory measurements, by visit. It will, however, be included in analyses of extreme values observed during a particular period of time, such as tabulations of high/low/out-of-range test results observed while a subject was on treatment. It will also be included in the analyses of endpoints that are not connected to a particular scheduled visit, such as, for instance, time to the first Lisinopril/Valsartan dose decrease after randomization.

3.3.4 Multiplicity / Multiple Comparisons

Statistical testing will be performed for all primary and secondary hypotheses. In all cases, the null hypothesis will be that of no difference between the treatment arms (SZC vs placebo), with the two-sided alternative of there being a difference. Two primary hypotheses (corresponding to the evaluation of the difference in total and chronic eGFR slope, respectively) are defined in the study.

The family-wise Type I error rate will be controlled in the strong sense over the families of primary and the secondary hypotheses i.e., regardless of whether the hypotheses covered are true or false.

Two co-primary hypotheses (corresponding to the evaluation of the difference in total and chronic eGFR slope, respectively) are defined in the study. The two hypotheses will be tested in parallel (i.e., with no pre-defined order) using the whole significance level alpha.

Provided both primary hypotheses are rejected, the testing will proceed to the secondary hypotheses. A fixed sequence MTP will be applied to the family of all secondary hypotheses, with the order in the sequence following the order specified in Table 2.

In accordance with the fixed sequence MTP, significance for a hypothesis will be declared if the corresponding two-sided p-value is smaller than 0.05, provided that all other preceding hypotheses in the sequence have been rejected.

3.3.5 Handling of Protocol Deviations in Study Analysis

Reasons for PD being classified as Important Protocol Deviations (IPD) will include those related to:

- Inclusion criteria
- Exclusion criteria
- Discontinuation criteria for IP met but subject not withdrawn from study treatment
- Discontinuation criteria for overall study withdrawal met but subject not withdrawn from study
- IP related deviations
- Excluded medication taken
- Deviations related to study procedure
- Incorrect stratification
- Other important protocol deviations

Details regarding protocol deviations, including a finer sub-categorization, as well as methods of detection, will be listed in the Protocol Deviation plan. Since an intention-to-treat principle is applied to the main analyses of the efficacy endpoints, occurrence of an IPD will not imply exclusion of data from these main analyses. However, supplementary analyses to evaluate e.g., the impact of usage of disallowed medications on the efficacy results, might be conducted, and would then exclude data points obtained while a subject is taking such a disallowed medication (see Section 4.2.7 for details).

Deviations related to the Covid-19 pandemic will be identified during the IPD collection.

4 STATISTICAL ANALYSIS

This section provides information on definitions, derivations, analyses, and data presentations per domain (study population, efficacy, safety).

4.1 Study Population

This section, "study population", covers presentation of subject disposition, analysis sets, protocol deviations, demographics, baseline characteristics, medical history, concomitant medication, and study drug compliance.

Unless specified otherwise, analyses will be performed separately for the initiation, run-in and maintenance phases, using the SAS-IP and SAS-RIP for first two phases, and the full analysis set for the maintenance phase.

Data will be summarised descriptively for each of the phases, by treatment arm (for the maintenance phase) and the overall total population. Categorical variables will have an additional "Missing" category that includes the subjects for which the relevant information is not available. Denominators used to calculate percentages will be the number of subjects in the relevant analysis set and in total (i.e., "missing" category included in the denominator).

4.1.1 Subject Disposition and Recruitment

4.1.1.1 Definitions and Derivations

Subject disposition will be collected as part of the eCRF. The following definitions and derivations are applicable for the table:

- **Enrolled** subjects will be defined as those who have signed the informed consent form.
- Subjects who **entered the initiation phase** will be defined as those who received at least one dose of Initiation SZC.
- Subjects who **entered the run-in phases** will be defined as those who received at least one dose of Run-in SZC or Run-in RAASi (lisinopril/valsartan/irbesartan).
- Subjects who **entered the maintenance phase** will be defined as those who were randomized.
- Subjects who **completed a phase of the study** will be defined as subjects who either are assigned the status "Completed" for the phase by the investigator, or who have a

disposition status as per the eCRF (e.g., "Death", "Withdrawal by subject") that is assigned during a later phase.

- Subjects who **completed the study** will be defined as subjects who completed all these four phases:
 - the Screening phase,
 - the Initiation phase,
 - the Run-in phase, and
 - the Maintenance phase,and, in addition, attended the follow-up visit.
- Subjects who **completed treatment** for a given phase will be defined as subject who did not discontinue treatment prematurely during that phase. Note that, for the initiation and run-in phases, this should coincide with completion of that whole phase, as subjects who discontinue treatment during these phases should also discontinue the whole study as per the study design.

The study period during which a particular disposition event takes place is also indicated directly in the eCRF by the investigators and will be used in the presentations.

